*** Continuing Review ***

Continuing Review Request

WHAT TO UPLOAD WITH YOUR CONTINUING REVIEW APPLICATION

For studies where research activities are limited to data analysis, upload subject safety information and publications (e.g., manuscripts, abstracts) since the last IRB approval, if applicable.

NOTE: if activities are limited to data analysis of de-identified/anonymous data (data that can no longer be linked to subject identifiers directly or through use of a code with master list kept), the study can likely be closed via the Final Report Form. See the SLU IRB Guidance for Closure of Human Subjects Research Studies.

For all other studies, upload:

- Subject safety information including the most current Serious Adverse Event (SAE) cumulative table and data safety monitoring reports since the last IRB approval, if applicable.
- Any publications (e.g., manuscripts, abstracts) since the last IRB approval.

Any changes, updated and/or new study materials should be uploaded and questions 19 - 24 of this form should be completed.

1. Please indicate the status of the study:

a) The study has not started but will become active.
Please explain why the study has not started.

b) X The study is ACTIVE (please check the appropriate box below):
 X Study is open to accrual.
 X Study is on hold or halted.
Please explain what needs to occur before accrual can resume.
Study is permanently closed to accrual.

i. Have all subjects completed all research related activities/interventions?

Protocol Title: Conservative versus Suture Repair of Hand and Feet Lacerations in Children

- ii. Will the research only remain active for long-term follow-up of subjects?
- iii. Are remaining research activities limited to data analysis only? (See instructions above).
- iv. For studies that are closed to subject accrual, do any subjects need to be re-consented (to inform them about changes to study procedures, study risks, study personnel, etc.)?

For IRB office use: * may qualify for expedited review

c) The study has expired and needs to be re-initiated.
Explain any research activities occurring during lapse in IRB approval.

2. Date the study was initially approved by the IRB: 06/21/2016

3. Approval date of previous continuing review: 06/05/2018

4. Total number of participants/records/specimens you are approved to enroll: 50

5. Total number of subjects that have given consent (verbal or written) to date: 26

6. Total number of subjects that failed screening (if not applicable, state N/A): 0

7. Total number of participants accrued since the beginning of the project: 26

8. For multi-center studies, number of subjects approved for accrual study-wide (SLU site plus all other sites):

9. For multi-center studies, number of subjects enrolled study-wide (SLU site plus other sites):

10. Number of withdrawals from the research and explanation/reasons for withdrawals.
N=9; Due to lack of patient returns at 4 months post repair for digital pictures to be obtained and for wound check

11. Description and number of:

Protocol Title: Conservative versus Suture Repair of Hand and Feet Lacerations in Children

a) Reportable Protocol Deviations/Violations since the last approval date:

none

b) Unanticipated Problems (UPs) since the last approval date:

none

c) Serious Adverse Events (SAEs) since the last approval date: Note: Information here should be consistent with the cumulative table, which should also be attached in section #16.

none

12. Have there been any complaints about the research during the last year?

N

If yes, please describe.

13. Briefly describe the progress of the study to date. Provide a status of participants in study, for example, where is the most recently accrued participant in terms of timeline in the study? If participants are in long-term follow-up, explain what this consists of in terms of data collection and/or intervention. Provide any new information in regard to risks. Summarize or attach publications or presentations.

Lack of patient follow up has hampered the progress of the study

14. Is there a Data Safety Monitoring (DSM) plan for this study?

Y No

Yes, a copy of the DSM report(s) for the last approval period is attached.

Yes, but a copy of the DSM reports(s) for the last approval period is not attached. Please explain below.

15. FDA Regulated Studies

Is this a Food and Drug Administration (FDA) Regulated Study, (i.e., involves drugs, N devices, biologics)? If yes, please answer the following questions:

a) Have there been any changes in the FDA status of any drug or device used in the study?

If yes, please explain:

b) Have any of the investigational drugs or devices used in this study received FDA approval?

If yes, please explain:

Protocol Title: Conservative versus Suture Repair of Hand and Feet Lacerations in Children

c) Have any new alternative drugs or devices been approved for treatment of the study condition that may affect subjects willingness to participate?

If yes, please explain:

Have current subjects been notified? Please explain:

d) Has there been a change in the standard care that may be considered as an alternative to the investigational drug or device or that would affect the original study design?

If yes, please explain:

Have current subjects been notified? Please explain:

e) Is there any new information that might affect the risk/benefit ratio and the willingness of current study subjects to participate or to continue to participate in the research?

If yes, please explain:

Have current subjects been notified? Please explain:

f) Does the study include an investigator's brochure (IB)?

If yes, what is the current version date?

(If study has multiple IBs, attach current versions in Attachments section (#16))

16. Provide a summary of any recent findings, literature, or other relevant information (especially pertaining to risks), if applicable.

none

17. Have there been any significant amendments or revisions to the protocol during the past approval period? (Significant amendments

N

Protocol Title: Conservative versus Suture Repair of Hand and Feet Lacerations in Children

include changes in study design or risk level including those that resulted in a change in consent).

If yes, please briefly summarize the changes:

18. The consent materials attached to this eIRB application (including consent documents, assent documents, recruitment statements or other materials used to obtain consent) are the versions being used in the conduct of this study and all enrolled subjects have signed consent forms on file, if required. (If the requirement to obtain consent was waived or if no participants have enrolled since last continuing review, check N/A).

NOTE: The IRB routinely monitors consent document usage and may request copies of redacted participant consent forms.

19. Are any changes (amendments) requested with this Continuing Review?

Yes, please complete the remainder of this form.
No, form is complete. Please submit.

20. Summarize the proposed changes to the protocol in lay terms, including the type of change AND what the change involves.

If this is a change in PI a new Department Chair review is required. Please upload the signed document in the Attachments section.

In order to salvage this study may have to look at crowd sourcing evaluation tools such as Amazon's Mechanical Turk(1) where photos of repaired wounds of the hand and feet (suture vs no suture) at 4 months could be compared and rated by the lay public. This would be a form of data analysis and does not violate the study protocol

1. Crump MJ, McDonnell JV, Gureckis TM. Evaluating Amazon's Mechanical Turk as a tool for experimental behavioral research

21. Provide justification/explanation for the proposed changes.

Amazon Mechanical Turk (MT) is a crowd sourcing evaluation tool. For this study, sets of photographs of hands and feet lacerations (repaired/ no repaired) could be assessed as to cosmetic outcome or scar formation. Photographs would be grouped in terms of repair vs no repair but the crowd source would be blinded to the method of repair. In this way, we would use existing digital photographs of extremities already obtained by the study to evaluate the cosmetic outcome of extremity lacerations repaired vs no repair. In the original protocol, physician performed the evaluation of the digital images, with MT hundreds perhaps thousand of individuals will be evaluating the cosmetic outcome of the repair (or no repair) using a likert scale, assuming most participants are likely non-physician, this may result in a more accurate evaluation of a child's wound repair. MT participants are paid a few cents for their efforts since there are many surveys being conducted by Amazon.

22. Will currently accrued subjects need to be notified of changes?

N

If no, please justify why not.

No changes in the original IC only the way the data is being used. No confidential information is being used only digital images of subject repairs (ie hand and feet)

If yes, please explain how AND when notification or re-consenting will occur.

Protocol Title: Conservative versus Suture Repair of Hand and Feet Lacerations in Children

23. Does the SLU IRB Protocol need to be modified? N

24. Are consent documents modified? N

Proceed to the appropriate section(s) of the protocol and make your changes. Also make necessary changes in the Consent Form(s), Assent Form(s), Recruitment Statement, Questionnaire, or other attachments, as applicable. Upload any revised IRB materials. Please provide the entire revised document (not just revised pages). Use track changes or highlight (in yellow) changes to documents being revised. Please upload a tracked/highlighted copy of each revised document to be stamped upon IRB approval. NOTE: Upload a clean copy (changes or highlights removed) of documents in file formats other than Microsoft Word (i.e., the IRB will remove the tracked changes/highlights on uploaded Word documents).

NOTE: Protocol amendments must receive IRB review and approval before they are implemented, unless an immediate change is necessary to eliminate an apparent hazard to the subjects.

Sponsored Studies: Remember to update the Sponsor's Protocol version number and date in the Funding section of the protocol (this information will appear on the approval letter).

List of changed sections:

Personnel Information

Attachments (16)

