Patients will be asked to follow-up in the Pediatric Emergency Department in 10-14 days. The patients will have a reminder phone call on day 6-8 for their follow-up visit and arrange for an appointment time. The wounds will be evaluated for complications that were defined a priori as follows: "wound infection" was one that required systemic antibiotics as determined by the treating attending physician; and "wound dehiscence" as a wound that required the placement

Protocol Title:

Conservative versus Suture Repair of Hand and Feet Lacerations in Children

of additional sutures or tissue adhesives. Children in the suture repair group will have their sutures removed. Parents will fill out a follow-up survey at this visit (see Initial Follow-up Survey).

Follow up data will be obtained from the parent or care giver for all subjects in the form of a questionnaire, patient with healing laceration will return with the parent or guardian for inspection of the wound with possible suture removal at 10-14 days then a re-evaluation of the healing wound with digital pictures taken at 3-4 months post ED enrollment for both treatment groups.

Patients will be asked to follow-up in the Pediatric Emergency Department in 12-16 weeks from the initial presentation. The patient will have a reminder phone call in week 11 for this visit and arrangement with time. The parent will fill out a second survey (see Final Follow-up Survey). Photographs of the wound will be taken, using a standardized protocol with a dedicated digital camera, and then printed by a pre-assigned printer. These photographs will be loaded to a computer to prevent alterations.

The photographs will be rated by 3 pediatric emergency physicians on the research team blinded to the treatment assignments. Independent evaluations will enable us to assess inter-observer reliability. The previously validated Visual Analogue Scale (VAS) will be used to assess the cosmetic outcome. The frequently used scale is a 100mm continuous line that is marked on the right end with "best scar" and on the left with "worst scar". The observer will be asked to mark on the line where they believe the scar "best fits". If the patient does not appear for their follow-up visit, a phone call will be made to the parent or guardian, who will be asked to report their satisfaction of the wound on a scale of 1 to 10, with 1 being "very unsatisfied" and 10 being "very satisfied".

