4	Continuing Review	
Question 17 of the Continuing Review Form describes an amendment to the protocol that has not yet been submitted for review/approval. Please remove this information from Question 17 of the Continuing Review Form, and describe these requested change in questions 19-24 of the Continuing Review Form. In addition, please be sure to incorporate the changes throughout the protocol and consent documents, as applicable.
 
There is very limited information in question 17 regarding the proposed changes. Please be sure to describe the crowd-sourcing data considerations as it pertains to outcomes, consent changes, validity related to this type of wound repair. Please also describe how experimental design and primary/secondary outcomes for this study can incorporate the Amazon Mechanical Turk.
 
In addition, question 17 states the incorporation of mTurk is necessary in order to salvage this study. If these changes are not made, please describe how the study plans to accrue more subjects and obtain adequate follow-up data.
 
Done
	Y
5	Continuing Review	
Please provide an explanation as they why follow-up data was able to obtained for the first 18 subjects, but not for the last 9 subjects.
 
Uncertain as to why we could not get patients to return for a follow up 4 month visit, gift cards were still valid. It is this reason that we are changing the data analysis
	Y
3	Continuing Review	
Question 14 of the Continuing Review Form states there is no Data Safety Monitoring Plan for this study. However, section 9-11b of the protocol includes a plan for Data Safety Monitoring. Please revise the response to this question.
 
Since no further patient enrollment will take place and only the method of data analysis will change there is no further reason to have a DSM plan going forward
	Y
Additional Response by

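### If crowd raters see the photographs in sets by arm, hiding the repair method does not mask arm membership, and adding raters cannot remove a set impression they share; the proposal should specify single, intermixed, randomly ordered display.

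*Combined protocol and SAP*

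**What the plan says.** **Protocol, section 3(b).** The 3-4 month photographs are to be "rated by 3 pediatric emergency physicians on the research team blinded to the treatment assignments". The evaluations are independent, on a 100 mm VAS. Grouping by arm is not mentioned.

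**Continuing Review form, question 20.** To rescue the study, photographs of the wounds ("suture vs no suture) at 4 months could be compared and rated by the lay public") may be put on a crowd-sourcing platform.

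**Continuing Review form, question 21.** The objects to be rated are described as "sets of photographs of hands and feet lacerations (repaired/ no repaired) could be assessed as to cosmetic outcome or scar formation". The next sentence is "Photographs would be grouped in terms of repair vs no repair but the crowd source would be blinded to the method of repair". The rating is made "using a likert scale". The stated gain comes from numbers: "with MT hundreds perhaps thousand of individuals will be evaluating the cosmetic outcome", and "this may result in a more accurate evaluation of a child's wound repair". The form mentions no random order, mixing of arms, single-photograph rating or analysis that allows for grouping. Question 23 says that the protocol itself needs no modification.

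**Comments, items 3 and 5.** The sponsor replies that enrolment will not continue and, on the missing 4-month visits, "It is this reason that we are changing the data analysis".

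**Event History.** Approval expired on 06/21/2019 and the form was withdrawn on 09/30/2019.

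**The concern.** Blinding of an outcome rater has to hide which photographs belong together, as well as the name of the treatment. A rater who sees one arm's wounds side by side can form one impression of the set. A single striking scar, or a different mix of hands and feet, can then colour the scores of its neighbours. A scar that gives away its method, for example through stitch marks, gives away the whole set.

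Such an error is common to every photograph in the arm. If raters share it, it is also common to the raters. Averaging over a large crowd removes the noise of individual raters but leaves this part untouched. A test that compares two arm means cannot tell it from a treatment effect, because its standard error is built from the spread within each arm.

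At stake is the primary cosmetic comparison. The crowd rating is offered as the way to save it, and its apparent precision would partly reflect how the pictures were laid out. Compared with the independent blinded rating in section 3(b), this would weaken the safeguard.

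**Working it through.** **1. The text.** Three features of questions 20 and 21 point to display by arm. The thing assessed is a set labelled by repair status. The photographs are to be compared as well as rated. The blinding clause is joined by a *but*, which qualifies what raters see and would be unnecessary if grouping happened only at analysis. None of this is conclusive.

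**2. Inputs.**
- From section 3(d): 18 per group, 90% power, alpha 0.05, 15 mm difference, Student's t-test. No SD is stated.
- From the Continuing Review form: 26 accrued, 9 without the 4-month visit, so 26 − 9 = 17 photographed. The Board's comment (item 5) speaks of 18 with follow-up and 9 without.
- Assumed: a 9/8 split, a VAS-equivalent scale, and a shared set effect with SD *s* = 3, 5 or 8 mm in each arm. The documents give no figure for *s*.

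**3. SD implied by the plan's sample size.** Solving the two-sided 5% t-test (noncentral t) for 18 per group and 90% power at 15 mm gives SD = 13.48 mm. Other readings of the unstated sidedness and test give up to 15.4 mm (one-sided 0.05, normal formula). The 18 per group can therefore be matched but not verified.

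**4. Standard error that the test sees (negligible rater noise).** SE² = SD² × (1/n₁ + 1/n₂) = 13.48² × (1/9 + 1/8) = 181.7 × 0.2361 = 42.9, so SE = 6.55 mm.

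**5. True error of the nominal 5% test.** The arm difference has variance SE² + 2s². The t statistic is therefore too large by k = √(1 + 2s²/SE²). With 15 degrees of freedom the critical value is 2.131, so the true error is P(|t₁₅| > 2.131/k).

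| Set SD *s* | 2s² | k | 2.131/k | True two-sided error |
|---|---|---|---|---|
| 0 mm | 0 | 1.000 | 2.131 | 5.0% |
| 3 mm | 18 | 1.191 | 1.789 | 9.4% |
| 5 mm | 50 | 1.472 | 1.448 | 16.8% |
| 8 mm | 128 | 1.996 | 1.068 | 30.2% |

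Simulation of 100,000 trials agrees to within about 0.2 percentage points. With SD = 15.4 mm the same formula gives 8.4%, 14.2% and 25.8%. With 9/9 children and 13.48 mm it gives 9.7%, 17.6% and 31.5%.

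**6. Effect of the number of raters R.** Add an assumed rater SD of 20 mm, take a child SD of 13.9 mm (two-sided normal formula), and set *s* = 5 mm:
- The test sees SE² = (13.9² + 20²/R) × 0.2361.
- The true variance adds 2 × 5² = 50, which has no 1/R term.

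| Raters | SE the test sees | True SE | True two-sided error |
|---|---|---|---|
| 3 | 8.78 mm | 11.27 mm | about 12% |
| 1000 | 6.76 mm | 9.78 mm | about 16% |

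More raters do reduce the total error. They reduce the reported error proportionately more, so the test becomes less honest as the crowd grows. With no set effect it stays at about 5% for either number of raters.

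**The case against.** The strongest reply is that display by arm is inferred. The sentence can mean that ratings are grouped by arm for analysis while raters see unmarked pictures, and comparison could mean pairs or sets that contain both arms. This stands as a possible reading. It does not remove the point, because the form gives no display rule at all and its wording leans the other way.

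Several stronger readings are tempting, and the documents do not support them:

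- **That grouping by repair status sorts children by treatment received.** A reader might infer that a conservative-arm wound closed later, which the dehiscence definition in section 3(b) allows for, would move to the other set. But sections 1(a) and 2(a) use repair and non-repair as names for the two approaches, and no such wound is reported. Using the packet allocation is only a precaution.
- **That the number of raters makes no difference.** Only a set error common to all raters persists. Impressions that differ from rater to rater, for instance through viewing order, do average out.
- **That the percentages estimate this trial's error.** The set SDs and the 9/8 split are assumed, the scale is a VAS while the crowd would use a Likert scale, and the t-test is borrowed from section 3(d) because the form names no test for crowd ratings.
- **That this is an approved plan.** The wording is tentative, the Board deferred the submission on July 2, 2019 and asked for more detail on the crowd-rating design, and the form was withdrawn. The protocol still specifies three blinded physicians.

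**Conclusion.** The point holds in conditional form. If the crowd sees photographs in sets by arm, concealing the method is not enough to blind the rating, and a set impression shared by raters survives any number of them. That conclusion does not depend on the assumed figures.

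Its size is unknown. Under the assumptions above, a 5% two-sided test would have a true error of about 9%, 17% or 30% for a shared set SD of 3, 5 or 8 mm, or 8%, 14% and 26% with the larger SD of 15.4 mm. No such figure can be given for the Likert scale, which has no stated SD or margin.

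If the sponsor meant grouping only at analysis, the display problem disappears and a clear statement of the display rule is all that is needed. Given the withdrawal, this is a correction to make before any resubmission or use of crowd rating. It is not a fault in an operative plan.

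**What to change.** If crowd rating is resubmitted or used, replace the grouping sentence in question 21 with a display and analysis rule, and carry it into sections 3(b) and 3(d):

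- Each photograph is shown singly and unlabelled, with hands, feet and both arms intermixed, in a fresh random order for each rater.
- The arm is attached only after rating is complete, using the randomised packet allocation.
- The child is the unit of analysis: average the ratings per child before comparing arms, or use a mixed model with child and rater effects.

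The only cost is survey set-up and a few sentences of text. A telling scar may still reveal its own method, but it would no longer identify the rest of its arm. The change does nothing about the small number of children. Even with no set effect and no rater noise, the SE in the illustration is 6.55 mm, and no crowd size lowers it.

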
Please save frequently

b) Describe any animal experimentation and findings leading to the formulation of the study, if

Protocol Title: Conservative versus Suture Repair of Hand and Feet Lacerations in Children

there is no supporting human data.

n/a

2. Purpose of the study

a) Provide a brief lay summary of the project in <200 words. The lay summary should be readily understandable to the general public.

The purpose of this study is to compare outcomes of 2 repair methods in simple (<2cm) hand and feet lacerations in the pediatric population (2-17 yrs). Our hypothesis is that there is no statistical difference in cosmetic outcomes between suture repair and non-repair of these injuries. This study has been performed in the adult population, but has not yet been done in children. We would like to be the first to show that conservative repair can be done in our pediatric population. The suture group will have their injuries repaired with non-absorbable sutures (nylon) which remain the gold standard in cosmetic repair of hands and feet. The conservative group will have identical cleaning and preparation of the wound, but the laceration will be covered with antibiotic ointment and sterile gauze without repair. Secondary outcome measure include patient satisfaction, infection rates, pain during repair, time of initial ED visit stay, and cost of supplies used in repair. Our patients will return in 7-10 and 14 days and in 3 months for evaluation. Wounds and scars will be evaluated at both 7-10 and 14 days and 3-4 months by both the researchers and the parents or care givers. A satisfaction survey will be administered to the parent or guardian. At 3-4 months, digital photographs of the healing lacerations will be graded for appearance by clinicians blinded to the repair method. The initial visit will be billed to their insurance and the follow-up visits will be free (non-registered).

Page numbers from a sponsor's protocol/grant may be referenced in 2b and 2c.

b) List your research objectives (specific aims & hypotheses of the study).

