Our primary hypothesis is that there is no difference in cosmetic outcomes between suture repair and conservative treatment of simple, superficial (<2cm) hand and feet lacerations in the pediatric population. Secondary measures will be infection rates, pain scores, time to return to normal activity, time of initial ED visit, and cost of supplies used in repair. Our aim is to show that conservative repair saves time, money and reduces patient pain compared to traditional suture repair, while having no decrease in cosmetic satisfaction or infection rates.

Please save frequently

c) Describe the study design (e.g., single/double blind, parallel, crossover, control, experimental, observational, etc.). If the study is investigator-initiated, a timeline for individual subject recruitment, follow-up, and analysis for the study is required. Also, indicate if the subjects will be randomized.

We will use a prospective clinical trial with computer generated randomization to test our hypothesis. Patients will be recruited by a qualified pediatric emergency physician. Once consent is obtained from the parent(s)/legal guardians, patient data will be collected. The patient will have their hand or foot laceration(s) treated in the emergency department at that time by an attending physician, PEM fellow, or senior resident. The patient will then follow-up in 10-14 days for a wound check and satisfaction survey, and then again at 3-4 months for repeat survey and photograph of the healed wound. Our timeline for recruitment is approximately 15-18 months, 12-15m for recruitment, plus 3 months for additional follow-up visits. Analysis of the data should take an additional month.

Protocol Title: Conservative versus Suture Repair of Hand and Feet Lacerations in Children

d) If subjects will be given placebo, please justify placebo use. *?HELP?*

There will be no placebos used in this study.

3. Study Procedures

a) N Is this project a multicenter study (i.e., same project is conducted elsewhere by a different investigator) OR does this study involve conduct of research at multiple sites? Is SLU acting as a coordinating center for other sites OR is the SLU PI a direct recipient of a federal grant for this research? If yes, complete and attach the Supplemental Application for Coordinating Center Activities.
Will the SLU site be participating in all parts/procedures/arms of the study?
If No, explain what SLU will NOT participate in:

Please save frequently

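### Does the proposal for lay crowd rating on a Likert scale leave the trial without a usable 15 mm criterion?

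*Combined protocol and SAP*

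**What the plan says.** The primary objective in section 2(b) is cosmetic: "Our primary hypothesis is that there is no difference in cosmetic outcomes between suture repair and conservative treatment". Section 2(a) says that "digital photographs of the healing lacerations will be graded for appearance by clinicians blinded to the repair method", and section 3(b) adds that "The photographs will be rated by 3 pediatric emergency physicians on the research team blinded to the treatment assignments". The instrument in section 3(b) is a 100 mm line running from worst to best scar. Section 3(d) sets 15 mm on that line as the margin, cites minimal important differences of 10 to 15 mm, and sizes the trial at 18 per group on the same 15 mm. The test is an independent-samples t-test.

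The third Continuing Review form, submitted in June 2019 and again in July 2019, adds something else. Question 20 opens with "In order to salvage this study may have to look at crowd sourcing evaluation tools" and continues that "This would be a form of data analysis and does not violate the study protocol". Question 21 describes the raters and the scale: "with MT hundreds perhaps thousand of individuals will be evaluating the cosmetic outcome of the repair (or no repair) using a likert scale". Question 23 reads "Does the SLU IRB Protocol need to be modified? N". The form's own note on amendments says "Protocol amendments must receive IRB review and approval before they are implemented".

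**The concern.** A margin in millimetres of a visual analogue scale has no meaning on a Likert scale of unknown length. If the crowd score became the main cosmetic result, the primary hypothesis could not be tested against the margin the protocol sets. A margin picked after the ratings were seen would not be prespecified.

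Two further points add weight. The answer to question 23 sits badly with protocol sections that still describe physician grading. The form also does not say how many ratings of one photograph would become one value per child, although the t-test and the sample size in section 3(d) count children.

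**Working it through.** **1. The units in the plan of record.** The inputs from sections 3(b) and 3(d) are: scale 100 mm; margin 15 mm; cited important difference 10 to 15 mm; 18 per group; power 90%; alpha 0.05. No standard deviation is stated, so 18 cannot be reproduced independently. It can be solved backwards. With n per group = 2 (1.960 + 1.282)² SD² / 15² = 21.02 × SD² / 225:

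- SD 13.5 mm: 21.02 × 182.25 / 225 = 17.03, rounded up to 18.
- SD 13.85 mm: 21.02 × 191.82 / 225 = 17.92, rounded up to 18.

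So 18 per group fits an SD of about 13.5 to 13.85 mm at two-sided 0.05 (about 14.95 to 15.35 mm at one-sided 0.05). Scale, margin, important difference and sample size are all in one unit.

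**2. What the margin would be on a Likert scale.** The form gives neither points nor anchors. If a 1-to-k scale were mapped linearly onto 0–100, the equivalent of 15 mm is 0.15 × (k − 1):

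| Scale | Calculation | Margin (points) |
|---|---|---|
| 1–5 | 0.15 × 4 | 0.60 |
| 1–7 | 0.15 × 6 | 0.90 |
| 1–10 | 0.15 × 9 | 1.35 |

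The documents support none of these mappings. The table shows only that no bar exists until the scale is fixed.

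**3. The status of the proposal.** From the Event History and Comments:

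- 06/09/2019: form submitted.
- 06/21/2019: protocol approval expired.
- 07/02/2019: the Board deferred the form. Comments item 1 states that analysis, among other activities, must stop during the lapse.
- 07/29/2019: form resubmitted.
- 09/30/2019: form withdrawn. No approval of it is recorded.

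**4. Question 23 against the protocol.** The form lists only Personnel Information and Attachments as changed. Sections 2(a), 3(b) and 11(g) still have clinicians or physicians grade the photographs, and section 3(d) still holds the 15 mm criterion. Had the crowd score been adopted as the primary measure, the negative answer would have been wrong. Since it was not adopted, the unchanged sections are what should stand.

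**5. The effect on the planned analysis.** An analyst who follows sections 3(b) and 3(d) takes the physicians' scores in millimetres and compares the arms against 15 mm. Nothing in that step uses a Likert score. Stating that the physician scale stays primary would repeat what those sections already say. A Likert margin, a rule for averaging crowd ratings and a new answer to question 23 would complete a form that is no longer before the Board.

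**The case for a change.** The strongest reply is that the investigators meant it. Their answers in the Comments are firmer than question 20: item 3 says enrolment is over and only the analysis method will change, and item 5 says the analysis is being changed because patients did not return. Question 21 sets crowd rating against the physician rating of the protocol, which reads as replacement. The Board asked in item 4 how the primary and secondary outcomes would take in the tool, and asked for edits throughout the protocol. The recorded reply is a single word saying this was done, yet sections 3(b) and 3(d) show no such edit. The photographs were taken for the study and the same text could be submitted again.

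All of that stands as a description of the form. It does not make the proposal operative. The approval step that it would have to pass is the one at which the Board had already asked about outcomes, validity and protocol edits. The specific points the Board did not name are the margin and one score per child.

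Two related arguments carry less weight. An inflated error rate from treating every crowd rating as independent would test an analysis nobody proposed. Question 20 speaks of photographs being compared, and question 21 of sets grouped by repair method, so it is not even clear that each photograph would get its own score. Loss of power is a separate matter. More raters do not add children, and the shortfall comes from accrual and follow-up: 26 consented of 50 approved, and 26 − 9 = 17 remaining by question 10. Comments item 5 instead has 18 followed and 9 not, which sums to 27.

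**Conclusion.** No change to the plan follows. The missing margin is a true gap in a tentative proposal that was deferred and then withdrawn. The plan of record has its raters, scale and 15 mm margin in matching units, and the effect on its primary comparison is nil. This rests on the Event History being complete, with no later approval of crowd rating outside these documents. Consent texts were not available, so the form's answer on consent is not judged.

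The point is worth keeping as a note for any resubmission. It would then need to say whether the crowd score supports or replaces the physician scale. It would also need to fix scale and margin before any rating is collected, reduce the ratings to one score per child, and answer question 23 to match.
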